11.4 Data Submission

Once a subject is confirmed and registered to the study, eCRFs should be submitted according to the detailed data submission guidelines (provided in a separate document). Generally, all data are due at the end of each cycle.

11.5 Data Management and Monitoring/Auditing

This study will be conducted in compliance with the Data Safety Monitoring Plan (DSMP) of the Robert H. Lurie Comprehensive Cancer Center of Northwestern University (please refer to Appendices for additional information). The level of risk attributed to this study

NU Study Number: NU 16B07
Other Study Number: CA 209-782

requires high monitoring, as outlined in the DSMP. The assigned QAM, with oversight from the Data Monitoring Committee, will monitor this study in accordance with the study phase and risk level.

This study will be conducted in compliance with the Data Safety Monitoring Plan (DSMP) of the Robert H. Lurie Comprehensive Cancer Center of Northwestern University (please refer to NOTIS for additional information). The level of risk attributed to this study requires High Intensity Monitoring as outlined in the DSMP. The assigned QAM, with oversight from the Data Monitoring Committee, will monitor this study in accordance with the study phase and risk level.

Once a subject is confirmed and registered to the study, eCRFs should be submitted according to the detailed data submission guidelines (provided in a separate document).

11.6 Adherence to the Protocol

Except for an emergency situation in which proper care for the protection, safety, and well-being of the study patient requires alternative treatment, the study shall be conducted exactly as described in the approved protocol.

11.6.1 Emergency Modifications

Investigators may implement a deviation from, or a change of, the protocol to eliminate an immediate hazard(s) to trial subjects without prior IRB approval.

For any such emergency modification implemented, an IRB modification form must be completed within 5 business days of making the change, and the QAM must be notified within 24 hours of such change.

11.6.2 Other Protocol Deviations

All other deviations from the protocol must be reported to the assigned QAM using the appropriate form.

A protocol deviation is any unplanned variance from an IRB approved protocol that:

- Is generally noted or recognized after it occurs.
- Has no substantive effect on the risks to research participants.
- Has no substantive effect on the scientific integrity of the research plan or the value of the data collected.
- Did not result from willful or knowing misconduct on the part of the investigator(s).

A protocol deviation may be considered an instance of Promptly Reportable Non-Compliance (PRNC) if it:

- Has harmed or increased the risk of harm to one or more research participants.
- Has damaged the scientific integrity of the data collected for the study.
- Results from willful or knowing misconduct on the part of the investigator(s).
- Demonstrates serious or continuing noncompliance with federal regulations, State laws, or University policies.

11.7 Investigator Obligations

The Principal Investigator is responsible for the conduct of the clinical trial at the site in accordance with Title 21 of the Code of Federal Regulations and/or the Declaration of Helsinki. The PI is responsible for personally overseeing the treatment of all study patients. The PI must assure that all study site personnel, including sub-investigators and

NU Study Number: NU 16B07
Other Study Number: CA 209-782

other study staff members, adhere to the study protocol and all FDA/GCP/NCI regulations and guidelines regarding clinical trials both during and after study completion.

The Principal Investigator at each institution or site will be responsible for assuring that all the required data will be collected, entered onto the appropriate eCRFs, and submitted within the study-specific timeframes. Periodically, monitoring visits may be conducted and the Principal Investigator will provide access to his/her original records to permit verification of proper entry of data. The study may also be subject to routine audits by the Audit Committee, as outlined in the DSMP.

11.8 Publication Policy

This section should be removed if the trial is not rated as a high intensity trial. All potential publications and/or data for potential publications (e.g. manuscripts, articles, data, text, digrams, abstracts, posters, charts, slides, picture, or clinicaltrials.gov releases) must be approved in accordance with the policies and processes set forth in the Lurie Cancer Center DSMP. For trials that require high intensity monitoring, the assigned QAM will prepare a preliminary data summary (to be approved by the DMC) no later than 3 months after the study reaches its primary completion date (the date that the final subject is examined or receives an intervention for the purposes of final data collection for the primary endpoint). If the investigator's wish to obtain DMC-approved data prior to this point (or prior to the point dictated by study design), the PI must send a written request for data to the QAM which includes justification. If the request is approved, data will be provided no later than 4 weeks after this request approval. The data will be presented to the DMC at their next available meeting, and a final, DMC-approved dataset will be released along with any DMC decisions regarding publication. The investigators are expected to use only DMC-approved data in future publications. The investigators should submit a copy of the manuscript to the biostatistician to confirm that the DMC-approved data are used appropriately. Once the biostatistician gives final approval, the manuscript may be submitted to external publishers.

NU shall provide BMS with a copy of each Publication at the earliest practicable time, but in any event not less than thirty (30) days prior to its submission to a journal, publisher or meeting or fifteen (15) days prior to any public disclosure of any manuscript or other public disclosure (e.g., presentations). To the extent applicable, BMS personnel shall be acknowledged (including authorship where applicable) in accordance with customary scientific practice.

REFERENCES

1. Factsheets SCS. Breast Cancer. National Cancer Institute. Bethesda, MD. 2015.
3. Haagensen CD. Diseases of the female breast. *Trans N Engl Obstet Gynecol Soc.* 1956;10:141-156.

Appendix A.

Common Terminology Criteria for Adverse Events V4.0.3 (CTCAE)

The descriptions and grading scales found in the revised NCI Common Terminology Criteria for Adverse Events (CTCAE) version 4.0.3 will be utilized for adverse event reporting. (<http://ctep.cancer.gov/reporting/ctc.html>)

NU Study Number: NU 16B07
Other Study Number: CA 209-782

Appendix B – ECOG Performance Status

The Eastern Cooperative Oncology Group (ECOG) performance status scale	
Grade	Description
0	Normal activity. Fully active, able to carry on all pre-disease performance without restriction.
1	Symptoms, but ambulatory. Restricted in physically strenuous activity, but ambulatory and able to carry out work of a light or sedentary nature (e.g., light housework, office work).
2	In bed <50% of the time. Ambulatory and capable of all self-care, but unable to carry out any work activities. Up and about more than 50% of waking hours.
3	In bed >50% of the time. Capable of only limited self-care, confined to bed or chair more than 50% of waking hours.
4	100% bedridden. Completely disabled. Cannot carry on any self-care. Totally confined to bed or chair.
5	Dead.

* As published in Am. J. Clin. Oncol.: *Oken, M.M., Creech, R.H., Tormey, D.C., Horton, J., Davis, T.E., McFadden, E.T., Carbone, P.P.: Toxicity And Response Criteria Of The Eastern Cooperative Oncology Group. Am J Clin Oncol 5:649-655, 1982.* The Eastern Cooperative Oncology Group, Robert Comis M.D., Group Chair.

NU Study Number: NU 16B07
Other Study Number: CA 209-782

Appendix C – Contraception Requirements

Investigators shall counsel FOCBP and male subjects who are sexually active with FOCBP on the importance of pregnancy prevention and the implications of an unexpected pregnancy. Investigators shall advise FOCBP and male subjects who are sexually active with FOCBP on the use of highly effective methods of contraception. Highly effective methods of contraception have a failure rate of < 1% per year when used consistently and correctly.

At a minimum, subjects must agree to the use of two methods of contraception, with one method being highly effective and the other method being either highly effective or less effective as listed below:

HIGHLY EFFECTIVE METHODS OF CONTRACEPTION

- a) Male condoms with spermicide
- b) Hormonal methods of contraception including combined oral contraceptive pills, vaginal ring, injectables, implants, and intrauterine devices (IUDs) such as Mirena® by FOCBP subject or male subject's FOCBP partner. Female partners of male subjects participating in the study may use hormone based contraceptives as one of the acceptable methods of contraception since they will not be receiving study drug.
- c) Nonhormonal IUDs, such as ParaGard®
- d) Tubal ligation
- e) Vasectomy.
- f) Complete Abstinence*

*Complete abstinence is defined as complete avoidance of heterosexual intercourse and is an acceptable form of contraception for all study drugs. Subjects who choose complete abstinence are not required to use a second method of contraception, but female subjects must continue to have pregnancy tests. Acceptable alternate methods of highly effective contraception must be discussed in the event that the subject chooses to forego complete abstinence.

LESS EFFECTIVE METHODS OF CONTRACEPTION

- a) Diaphragm with spermicide
- b) Cervical cap with spermicide
- c) Vaginal sponge
- d) Male Condom without spermicide*
- e) Progestin only pills by FOCBP subject or male subject's FOCBP partner
- f) Female Condom*

[figure not shown]
*A male and female condom must not be used together

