3.1 Inclusion Criteria

3.1.1 Patients must have histologically or cytologically confirmed stage IV breast carcinoma with a previous clinical diagnosis of IBC based on the presence of inflammatory changes in the involved breast, such as diffuse erythema and edema (peau d'orange), with or without an underlying palpable mass involving the majority of the skin of the breast. Pathological evidence of dermal lymphatic invasion should be noted but is not required for diagnosis.

3.1.2 Patients must have local or metastatic recurrence of IBC after prior surgery.

3.1.3 Patients must have a metastatic tumor negative for HER2. The lack of HER2 overexpression by immunohistochemistry (IHC), is defined as 0 or 1+ where as hyperexpression is defined as 3+. If equivocal IHC, 2+, the tumor must be non-gene amplified by FISH performed upon the primary tumor or metastatic lesion (ratio <2 and HER2 copy number <4).⁴⁷

3.1.4 Patients may have measurable disease, defined as at least one lesion that can be accurately measured in at least one dimension in accordance with RECIST criteria v. 1.1 OR non-measurable tumors (see section 6.5).

NOTE: Non-measurable tumors are small lesions (longest diameter <10mm or pathological lymph nodes with ≥ 10 to <15 mm short axis). Bone lesions, ascites, pleural/pericardial effusions, lymphangitis cutis/pulmonitis, inflammatory breast disease, and abdominal masses (not followed by CT or MRI) are considered as non-measurable.

3.1.5 Patients must be in consideration for 1st line systemic therapy for recurrent IBC.

NOTE: Patients must not have received chemotherapy in the metastatic setting, but adjuvant treatment after surgery is acceptable.

3.1.6 Patients must have confirmed availability of archival or freshly biopsied tumor tissue meeting protocol-defined specifications prior to study enrollment.

3.1.7 Patients must be female and age ≥ 18 years.

3.1.8 Patients must exhibit an ECOG status of 0-1. ECOG performance status 2 and 3 will be allowed only if decline in performance status is thought to be directly secondary to breast cancer disease burden by treating physician.

3.1.9 Patients must have adequate organ and bone marrow function ≤ 14 days prior to registration, as defined below:

• leukocytes	$\geq 2,000/\text{mCL}$
• absolute neutrophil count	$\geq 1,500/\text{mCL}$, regardless of transfusion or growth factor support
• platelets	$\geq 100,000/\text{mCL}$, regardless of transfusion or growth factor support

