• total bilirubin	total bilirubin $\leq 1.5 \times$ institutional upper limit of normal (ULN) (except patients with Gilbert Syndrome or liver metastasis, who can have total bilirubin $< 3.0 \times$ ULN)
• AST(SGOT)/ALT(SPGT)	$\leq 2.5 \times$ institutional upper limit of normal (ULN) (or ≤ 5 times ULN in case of liver metastasis)
• creatinine	Serum creatinine of $< 3.0 \times$ ULN (upper limit of normal)

NU Study Number: NU 16B07
Other Study Number: CA 209-782

3.1.10 Patients with history of central nervous system (CNS) metastases are eligible if CNS disease has been stable for at least 6 weeks prior to study registration in the opinion of the investigator and do not require corticosteroids (of any dose) for symptomatic management.

NOTE: Patients are not required to have CNS imaging prior to study entry.

3.1.11 Females of childbearing potential (FOCBP) must have a negative serum or urine pregnancy test (minimum sensitivity 25 IU/L or equivalent units of HCG) within 72 hours of registration.

NOTE: A FOCBP is *any woman* (regardless of sexual orientation, having undergone a tubal ligation, or remaining celibate by choice) who meets the following criteria:

- *Has not* undergone a hysterectomy or bilateral oophorectomy
- *Has had* menses at any time in the preceding 12 consecutive months (and therefore has not been naturally postmenopausal for > 12 months)

3.1.12 FOCBP and men who are sexually active with FOCBP must agree to follow instructions for method(s) of contraception for the duration of treatment and the designated post-treatment period (see Appendix C for details on appropriate contraception methods)

3.1.13 Patients must have the ability to understand and the willingness to sign a written informed consent prior to registration on study.

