4.5 Concomitant Medications/Treatments

4.5.1 Permitted Medications

All treatments that the investigator considers necessary for a subject's welfare may be administered at the discretion of the investigator in keeping with the community standards of medical care. All concomitant medication will be recorded on the case report form (CRF) including all prescription, over-the-counter (OTC), herbal supplements, and IV medications and fluids. If changes occur during the trial period, documentation of drug dosage, frequency, route, and date may also be included on the CRF.

Subjects are permitted the use of topical, ocular, intra-articular, intranasal, and inhalational corticosteroids (with minimal systemic absorption). A brief (less than 3 weeks) course of corticosteroids for prophylaxis (eg, contrast dye allergy) or for treatment of non-autoimmune conditions (eg, delayed-type hypersensitivity reaction caused by a contact allergen) is permitted. Inhaled or topical steroids, and adrenal replacement steroid doses < 10 mg daily prednisone equivalent, are permitted in the absence of active autoimmune disease.

Concomitant palliative and supportive care for disease related symptoms (including bisphosphonates and RANK-L inhibitors) is allowed if initiated prior to first dose of study therapy.

Antihormonal therapy is permitted for patients with hormonal receptor positive IBC.

All concomitant medications received within 28 days before the first dose of trial treatment and 30 days after the last dose of trial treatment should be recorded. Concomitant medications administered after 30 days after the last dose of trial treatment should be recorded for SAEs.

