4.5.2 Prohibited Medications

Subjects are prohibited from receiving the following therapies during the Screening and Treatment Phase of this trial:

- Anti-cancer systemic chemotherapy or biological therapy
- Immunotherapy not specified in this protocol
- Chemotherapy not specified in this protocol
- Investigational agents other than nivolumab or ipilimumab
- Radiation therapy
- Corticosteroids are not permitted unless they fall under the criteria listed in 4.5.1

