If PD is confirmed at any time, see section 4.4 on how to determine whether patient can be considered for further treatment. If patient continues, scans should be obtained every 12 weeks until PD is confirmed by 2 consecutive scans.

⁴ CBC with differential will include WBC, ANC, ALC, Platelets, and Hemoglobin. It will be collected within 14 days of registration, every 14 days during cycles 1 & 2, and prior to each treatment thereafter (day 1, 29, 43, and 57 of each cycle).

⁵ Chemistry panel will include glucose, calcium, albumin, ALT, AST, sodium, potassium, total bilirubin, alk phos, and creatinine. It will be collected within 14 days of registration, every 14 days during cycles 1 & 2, and prior to each treatment thereafter (day 1, 29, 43, and 57 of each cycle).

⁶ Amylase and lipase will be assessed at screening and Day 1 of each cycle.

⁷ TSH will be tested at screening and Day 1 of each cycle. If TSH is abnormal, free T4 should be tested

⁸ Serum or urine test for females of child-bearing potential (FOCBP) within 72 hours of registration. FOCBP are also required to have a negative pregnancy test within 24 hours of starting nivolumab and Day 1 of each cycle.

⁹ Nivolumab will be administered IV at 240mg over 30 minutes every two weeks in combination with ipilimumab as follows:
Cycle 1, C2D1, & C2D15: 240mg over 30 minutes (-5 / +15 minutes) every 14 days.

Starting with Cycle 2 Day 29: 480mg over 60 minutes (-10 / +15 minutes) every 28 days until PD, intolerance, or withdrawal of consent.

¹⁰ Ipilimumab will be administered IV at 1mg/kg over 90 minutes every six weeks in combination with nivolumab. Dosing will be based on body weight measured every 6 weeks, prior to each ipilimumab infusion. Nivolumab will be given before ipilimumab.

¹¹ Archival tissue (or fresh tissue if not available) will be collected at baseline for all patients. If the patient agrees, additional tissue may be collected during biopsies performed as standard of care during study participation. Please see separate lab manual for details.

¹² Treatment will start within 14 days of registration, and continue until confirmed disease progression, unacceptable toxicity, or withdrawal of consent.

¹³ Study procedures may take place within 24 hours prior to study treatment.

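### Appendix C approves hormonal contraceptives for trial patients with no receptor condition, although receptor-positive patients can enrol and section 4.5.1 permits antihormonal therapy for them

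*Combined protocol and SAP*

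**What the plan says.** Five parts of the combined protocol and SAP bear on this.

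- **Criterion 3.1.12** makes contraception an entry condition: patients of childbearing potential "must agree to follow instructions for method(s) of contraception for the duration of treatment and the designated post-treatment period". It refers them to Appendix C.
- **Appendix C** requires two methods, at least one of them highly effective; complete abstinence may stand alone. Highly effective item (b) is "Hormonal methods of contraception including combined oral contraceptive pills, vaginal ring, injectables, implants, and intrauterine devices (IUDs) such as Mirena® by FOCBP subject". Less effective item (e) is "Progestin only pills by FOCBP subject or male subject's FOCBP partner". Both name the trial subject herself, and neither mentions receptor status.
- **Criterion 3.1.3** sets the only receptor restriction at entry: "Patients must have a metastatic tumor negative for HER2". Nothing in 3.1 or 3.2 excludes hormone-receptor-positive disease.
- **Section 4.5.1** anticipates such patients: "Antihormonal therapy is permitted for patients with hormonal receptor positive IBC".
- **Section 4.5.2**, which opens "Subjects are prohibited from receiving the following therapies during the Screening and Treatment Phase of this trial", lists chemotherapy, biological therapy, other immunotherapy, other investigational agents, radiation and most corticosteroids. It does not mention hormonal contraceptives.

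**The concern.** The protocol accepts hormone blockade as treatment for receptor-positive IBC, both during the study (4.5.1) and, where indicated, as adjuvant care (1.1). Appendix C nevertheless tells the same patients that a contraceptive hormone is an acceptable way to meet an entry criterion. The approval works against the treatment that the protocol allows.

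This is a stated approval rather than a missing detail. Site staff and patients will read the list as permission. If a patient acts on it, exposure could last as long as treatment, which continues until progression or intolerable toxicity (4.1). What is at stake is the care of a subgroup; the trial's inference is not affected.

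**Working it through.** **Text check.** The plan states no figure on this point, so there is none to reproduce. Take a patient of childbearing potential with receptor-positive, HER2-negative recurrent IBC.

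1. Entry: 3.1.3 is met, and no other criterion looks at hormone receptors.
2. Contraception: 3.1.12 sends her to Appendix C. Item (b) plus, for example, a diaphragm with spermicide satisfies the two-method rule.
3. Tumour treatment: 4.5.1 allows antihormonal therapy.
4. Prohibitions: neither 4.5.2 nor 3.2 limits the contraceptive.

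She complies throughout. The two-method rule can equally be met without hormones, for example by a nonhormonal IUD plus a diaphragm with spermicide, so the correction is feasible within the existing list.

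Item (b) also looks like untailored text. The only reason it gives for hormonal use concerns female partners of male subjects, who will not receive study drug, yet 3.1.7 admits women only.

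**How many patients could be receptor-positive.** The documents give no share for recurrent HER2-negative IBC. Two indirect sources bracket it.

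*Source 1, section 1.1.* ER is overexpressed in 30% to 44% of IBC in general. Metastases followed stage III disease in 35% of HR-positive and 56% of triple-negative patients. Assume that the ER share p holds within HER2-negative IBC and stands for HR-positivity.

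- Unweighted: 0.30 × 29 = 8.7; 0.44 × 29 = 12.8.
- Weighted by metastasis rate: share = 0.35p / [0.35p + 0.56(1 − p)].
  - p = 0.30: 0.105 / (0.105 + 0.392) = 0.105 / 0.497 = 0.211, and 0.211 × 29 = 6.1.
  - p = 0.44: 0.154 / (0.154 + 0.3136) = 0.154 / 0.4676 = 0.329, and 0.329 × 29 = 9.6.

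*Source 2, section 1.1.2.* Among 21 metastatic IBC patients with an actionable mutation, 28.5% were ER-positive/HER2-negative and 28.5% were negative for both. Within HER2-negative patients the share is 28.5 / (28.5 + 28.5) = 50%, and 0.50 × 29 = 14.5.

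| Assumed receptor-positive share | Of 29 | Of 15 (early stop) |
|---|---|---|
| 21.1% (1.1, weighted, p = 0.30) | 6.1 | 3.2 |
| 32.9% (1.1, weighted, p = 0.44) | 9.6 | 4.9 |
| 30% (1.1, unweighted) | 8.7 | 4.5 |
| 44% (1.1, unweighted) | 12.8 | 6.6 |
| 50% (1.1.2, selected subset) | 14.5 | 7.5 |

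The range is roughly 6 to 15 of 29. These counts are receptor-positive patients, not affected patients. The affected number is the count multiplied by the share of childbearing potential and by the share who would choose a hormonal method. The documents give neither share, so the product may be zero.

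**The case against.** The strongest case against has four parts.

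- **No documented harm.** The documents nowhere say that hormonal contraception is unsafe in receptor-positive disease. Section 4.5.1 only permits antihormonal therapy, and nothing distinguishes combined pills from a hormonal IUD or progestin-only methods. This stands as a limit: the point is an inference from the protocol's treatment purpose and can claim no size of harm. It does not remove the tension between approving a hormone and allowing hormone blockade in the same patient.
- **No contradiction.** Appendix C is a menu, and no patient is told to use a hormonal method. A reader might infer that the protocol contradicts itself; it does not, because both texts are permissive and can be followed together.
- **Clinical judgement would catch it.** Investigators counsel on contraception under Appendix C, 4.5.1 invokes community standards of care, and 11.7 has the principal investigator oversee treatment. A breast oncologist would probably steer the patient away. But these clauses are general, and the counselling clause promotes highly effective methods, a group that includes item (b). Consent pages are absent from the available copy, so whether they address this is unknown.
- **Fewer choices.** Removing hormonal methods could raise the risk of unintended pregnancy, and scheduled testing is sparse: "FOCBP are also required to have a negative pregnancy test within 24 hours of starting nivolumab and Day 1 of each cycle", with 12-week cycles. This is a fair caution, and it is why any switch must leave no gap in contraception.

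**Conclusion.** The concern holds as a low-severity patient-safety correction. Appendix C items (b) and (e) approve hormonal contraceptives for the trial subject without regard to receptor status, in a trial that admits receptor-positive patients and permits hormone blockade for them.

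Its size is unknown. The figure of about 6 to 15 receptor-positive patients among 29 assumes that all-IBC receptor shares, or those of a small subset selected for actionable mutations, carry over to this population. A reader might take it as a count of exposed patients or as a firm ceiling; the documents support neither.

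Two other stronger readings also fail. One is that hormonal methods should be barred when receptor status is unknown; nothing in the documents supports that breadth. The other is that the trial's results are compromised; the PFS endpoint, the 15 and 29 patient stages and the decision rules are untouched.

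**What to change.** Add one paragraph to Appendix C, with a cross-reference in 4.5.2 and matching consent wording:

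> Patients with hormone-receptor-positive disease, or on antihormonal therapy under 4.5.1, should use the listed non-hormonal methods (or complete abstinence) and not highly effective item (b) or less effective item (e). A patient already using a hormonal method switches as soon as feasible without a gap in contraception.

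Receptor status can be read from the pathology report already uploaded at registration (11.3), if the report gives it.

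The cost is fewer choices for these patients. Apart from sterilisation and abstinence, only the male condom with spermicide and the nonhormonal IUD remain as highly effective methods; the less effective list loses only item (e). A few patients may need to switch. The wording sets no fixed day because "Treatment will start within 14 days of registration" and the change should not be rushed at the expense of continuous contraception. No statistical section needs to change.
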